9.9 Data Handling and Record Keeping

9.9.1 Data Collection

All subject data relating to the trial will be recorded using an eCRF (conforms to 21 CFR Part 11 requirements [26]) unless transmitted to the Sponsor or designee electronically (e.g., laboratory data). The Investigator is responsible for verifying that data entries are accurate and correct by physically or electronically signing the eCRF.

The Investigator must maintain accurate documentation (source data) that supports the information entered in the eCRF.

The location of source data will be defined in the relevant source data location form prior to trial start.

The Investigator must ensure that the eCRFs are securely stored at the trial site in encrypted electronic form and are password-protected to prevent access by unauthorized third parties.

The Investigator must permit trial-related monitoring, audits, IRB review, and regulatory agency inspections and provide direct access to source data documents. This verification may also occur after trial completion. It is important that the Investigator(s) and their relevant personnel are available during the monitoring visits and possible audits or inspections and that sufficient time is devoted to the process.

The Sponsor or designee will provide the trial site(s) with secure access to and training on the electronic data capture application sufficient to permit site personnel to enter or correct information in the eCRFs on each subject.

An eCRF is required and must be completed for each enrolled subject. Screen failures and reasons for those will be captured in the eCRF system. The Investigator has ultimate responsibility for the accuracy, authenticity, and timely collection and reporting of all clinical, safety, and laboratory data entered on the eCRFs and any other data collection forms. Source documentation supporting the eCRF

data must indicate the subject's participation in the trial and must document the dates and details of trial procedures, AEs, other observations, and subject status.

The audit trail will show the user's identification information and the date and time of any correction. The eCRFs must be signed electronically by the Investigator to attest that the data contained on the eCRFs, including any changes made to the eCRFs, are correct and to endorse the final submitted data for the subjects for whom the Investigator is responsible.

The completed eCRFs are the sole property of the Sponsor and must not be made available in any form to third parties, except for authorized representatives of the sponsor or appropriate regulatory authorities, without written permission from the sponsor.

The Sponsor will retain the eCRF data and corresponding audit trails. A copy of the final archival eCRF in the form of a compact disc or other electronic media will be provided to the site for placement in the Investigator's trial file.

9.9.2 Database Management and Quality Control

Monitoring details describing strategy (e.g., risk-based initiatives in operations and quality such as risk management and mitigation strategies and analytical risk-based monitoring), methods, responsibilities, and requirements, including handling of noncompliance issues and monitoring techniques (central, remote, or on-site monitoring), are provided in the monitoring plan.

The Sponsor or designee is responsible for the data management of this trial, including quality checking of the data.

Trial monitors will perform ongoing source data verification to confirm that data entered into the eCRF by authorized site personnel are accurate, complete, and verifiable from source documents; that the safety and rights of subjects are being protected; and that the trial is being conducted in accordance with the currently approved protocol and any other trial agreements, ICH GCP, and all applicable regulatory requirements.

Records and documents, including signed ICFs, pertaining to the conduct of this trial must be retained by the Investigator for 25 years after trial completion unless local regulations or institutional policies require a longer retention period. No records may be destroyed during the retention period without the written approval of the sponsor. No records may be transferred to another location or party without written notification to the sponsor. The Investigator must ensure that the records continue to be stored securely for as long as they are maintained.

When subject data are to be deleted, the Investigator will ensure that all copies of such data are promptly and irrevocably deleted from all systems.

The Investigator(s) will notify the Sponsor or its designees immediately of any regulatory inspection notification in relation to the trial. Furthermore, the Investigator will cooperate with the Sponsor or its designees to prepare the Investigator site for the inspection and will allow the Sponsor or its designees, whenever feasible, to be present during the inspection. The Investigator site and Investigator will promptly resolve any discrepancies that are identified between the trial data and the subject's medical records. The Investigator will promptly provide copies of the inspection findings to the Sponsor or its

designee. Before response submission to the regulatory authorities, the Investigator will provide the Sponsor or its designees with an opportunity to review and comment on responses to any such findings.

During trial conduct, the Sponsor or its designees will conduct periodic monitoring visits to ensure that the protocol and ICH GCPs are being followed. The Monitors will review source documents to confirm that the data recorded on eCRFs are accurate. The Investigator and institution will allow the Sponsor's Monitors or designees and appropriate regulatory authorities direct access to source documents to perform this verification.

The trial site may be subject to review by the IRB, and/or to quality assurance audits performed by the Sponsor or companies working with or on behalf of the Sponsor, and/or to inspection by appropriate regulatory authorities.

It is important that the Investigator and their relevant personnel are available during the monitoring visits and possible audits or inspections and that sufficient time is devoted to the process.

9.9.3 Record Retention

To enable evaluations and/or audits from regulatory authorities or Sponsor, the Investigator agrees to keep records, including the identity of all participating subjects (sufficient information to link records, e.g., eCRFs, source documents), all original signed ICFs, eCRFs, SAE forms, source documents, detailed records of treatment disposition, and adequate documentation of relevant correspondence (e.g., letters, meeting minutes, telephone calls reports). The records must be retained by the Investigator according to the ICH, local regulations, or as specified in the Clinical Trial Agreement, whichever is longer.

If the Investigator becomes unable, for any reason, to continue to retain trial records for the required period (e.g., retirement, relocation), the Sponsor must be prospectively notified. The trial records must be transferred to a designee acceptable to the sponsor, such as another Investigator, another institution, or to the sponsor. The Investigator must obtain the Sponsor's written permission before disposing of any records, even if retention requirements have been met.

9.10 Source Documents

Source documents provide evidence for the existence of the subject and substantiate the integrity of the data collected. Source documents are filed at the investigator site.

Data entered in the eCRF that are transcribed from source documents must be consistent with the source documents or the discrepancies must be explained. The Investigator may need to request previous medical records or transfer records, depending on the trial. Also, current medical records must be available.

9.11 Trial and Site Closure

The Sponsor designee reserves the right to close the trial site or terminate the trial at any time for any reason at the sole discretion of the sponsor. Trial sites will be closed upon trial completion. A trial site is considered closed when all required documents and trial supplies have been collected and a trial-site closure visit has been performed.

The Investigator may initiate trial-site closure at any time upon notification to the contract research organization if requested to do so by the responsible IRB or if such termination is required to protect the health of trial subjects.

Reasons for the early closure of a trial site by the Sponsor may include but are not limited to:

- Failure of the Investigator to comply with the protocol, the requirements of the IRB or local health authorities, the sponsor's procedures, or GCP guidelines
- Inadequate recruitment of subjects by the Investigator
- Discontinuation of further trial intervention development

Trial termination information is also provided in the clinical trial agreement. If there is any conflict between the clinical trial agreement and this protocol, the clinical trial agreement will control as to termination rights.

9.12 Publication Policy and Public Disclosure

The Institution and the Investigator agree that the Sponsor shall have the sole and exclusive right to the first publication of the results of the trial.

The results of this trial may be published or presented at scientific meetings by the investigator after publication of the overall trial results or 1 year after end of the trial (or trial termination), whichever comes first.

The Investigator agrees to refer to the primary publication in any subsequent publications such as secondary manuscripts, and submits all manuscripts or abstracts to the Sponsor 30 days before submission. This allows the Sponsor to protect proprietary information and to provide comments and the Investigator will, on request, remove any previously undisclosed confidential information before disclosure, except for any trial or Sponsor intervention-related information necessary for the appropriate scientific presentation or understanding of the trial results.

For all publications relating to the trial, the Investigator will comply with recognized ethical standards concerning publications and authorship, including those established by the International Committee of Medical Journal Editors.

Authorship of publications for the overall trial results will be determined by mutual agreement and in line with International Committee of Medical Journal Editors authorship requirements.

If there are any discrepancies between the protocol and the clinical trial agreement regarding clinical trial-related publications, the provisions of the clinical trial agreement will prevail.

9.13 Protocol Compliance and Deviations

The Investigator must conduct the trial in compliance with the protocol provided by the Sponsor and given approval/favorable opinion by the IRB and the appropriate regulatory authorities. Modifications to the protocol must not be made without agreement between both the Investigator and the Sponsor. Changes to the protocol will require written IRB and the appropriate regulatory authority approval/favorable opinion prior to implementation, except when the modification is needed to eliminate an immediate hazard(s) to subjects. The IRB may provide, if applicable, regulatory authority permit, expedited review, and approval/favorable opinion for minor change(s) in ongoing trials that

have the approval/favorable opinion of the IRB. The Sponsor must ensure that all protocol modifications are submitted to the regulatory authority in accordance with the governing regulations.

If other unexpected circumstances arise that require deviation from protocol-specified procedures, the Investigator must consult with the sponsor (and IRB, as required) to determine the appropriate course of action.

The site must document all protocol deviations in the subject's source documents. In the event of a deviation expected to influence the subject safety or the estimation of the PK parameters, the site must notify the sponsor (and IRB, as required).

- Protocol deviations will be identified based on conditions related to the categories below:
- Protocol entry criteria
- Forbidden concomitant medications
- Missing evaluations for relevant endpoints
- Medications errors
- Other protocol deviations occurring during clinical trial conduct

All protocol deviations will be identified and listed where appropriate.

10 Safety

10.1 Safety Data Reporting and Collection Period

After signing informed consent, all AEs including SAEs and AESIs regardless of relationship to apraglutide will be collected, fully investigated and documented in source documents and eCRFs and will be reported either until the last protocol-specific procedure or safety follow-up.

Investigators should report any SAEs, or other AEs of concern that are believed to be related to apraglutide for up to 2 weeks following the safety follow-up visit (EOT).

Adverse events that occur between subject's ICF signature and dosing will be captured as pre-treatment AEs.

The Investigator must monitor the condition of the subject throughout the trial from the time of obtaining informed consent until the last protocol-specific procedure, whether it is the EOT visit or ET visit, or a safety follow-up period.

If an Investigator becomes aware of an SAE which occurred up to 2 weeks following the safety follow-up visit (EOT) (this includes withdrawn subjects) and he/she assesses the SAE to have a reasonable possible causality to the IMP, the case will have to be reported to the Sponsor via the Contract Research Organization (CRO) (Section [10.3.3](#)).

The emergency contact details for the Sponsor can be found in the Investigator Site File (ISF).

10.2 Definition and Assessment of (Serious) Adverse Events and Other Safety Related Events

An AE is any untoward medical occurrence in a subject or a clinical investigation subject administered a pharmaceutical product, and which does not necessarily have a causal relationship with the trial procedure. An AE can therefore be any unfavorable and unintended sign (including an abnormal laboratory finding), symptom, or disease temporally associated with the use of an IMP, whether or not related to the IMP [1]. Medical conditions present at the initial trial visit that do not worsen in severity or frequency during the trial are defined as baseline medical conditions (medical history) and are not to be considered AEs.

The sources of AEs include:

- The subject's response to questions about his/her health (a standard nonleading question such as "How have you been feeling since your last visit?" is asked at each visit)
- Symptoms spontaneously reported by the subject
- Investigations and examinations with findings that are assessed by the Investigator to be clinically significant
- Other information relating to the subject's health becoming known to the Investigator

For surgical or diagnostic procedures, the condition/illness leading to such a procedure is considered as the AE rather than the procedure itself.

Specific information related to liver safety can be found in Section [10.10](#).

An SAE is classified as any untoward medical occurrence that:

- Results in death
- Is life-threatening
- Requires in-patient hospitalization or prolongation of existing hospitalization
- Results in persistent or significant disability/incapacity
- Is a congenital anomaly/birth defect in a neonate/infant born to a mother exposed to apraglutide (also applies if father was exposed to apraglutide)
- Is a medically significant event in the Investigator's judgment (e.g., may jeopardize the subject or may require medical/surgical intervention to prevent one of the outcomes listed above) [27]

Events that Do Not Meet the Definition of an SAE:

- Elective hospitalizations to administer, or to simplify trial treatment or trial procedures are not considered SAEs. However, all events leading to unplanned hospitalizations or unplanned prolongation of an elective hospitalization (for example, undesirable effects of any administered treatment) must be documented and reported as SAEs
- Hospitalization or prolongation of hospitalization as part of a routine procedure
- Hospitalization for a survey visit, annual physicals or social reasons
- Hospitalization that does not include an overnight stay
- Elective hospitalizations for pre-existing conditions documented in the medical history that have not worsened
- Hospitalization to facilitate treatment of disease/illness with other treatment options, although these treatments are not permitted as per the protocol and will be documented as a protocol deviation

In case of doubt, an event should be reported within timelines.

Definition of Adverse Events of Special Interest

An AESI, serious or non-serious, is an AE of scientific and medical concern specific to the Sponsor's product or program, for which ongoing monitoring, additional information, and rapid communication by the Investigator to the Sponsor can be appropriate. Depending on the nature of the event, rapid communication by the trial Sponsor to other parties (e.g., regulators) might also be warranted in line with Council for International Organizations of Medical Sciences standards and local regulations.

The following are considered AESIs for this trial:

- Injection site reactions (ISR)
- Gallbladder, biliary, and pancreatic disease
- Fluid overload
- Hypotension
- Persistent abdominal pain

Injection site reactions

Subjects will be monitored for ISRs for at least 1 hour after IMP administration given at site, until the reaction stops. The individual symptoms of the ISR (e.g., injection site pain, injection site pruritus

[itching], injection site erythema [redness], injection site edema [swelling], injection site bruising) should be reported as AEs.

Data on local tolerability will be collected as an AESI. The following characteristics of ISRs will be documented:

- Pain
- Erythema
- Induration
- Pruritus
- Bruising

Severity and duration of these features of the ISR will be collected by the site by direct observation when IMP is administered on site. When IMP is administered at home, ISRs should be reported to the site for documentation in the subject's source documents and entry into the eCRF.

Gallbladder, Biliary and Pancreatic Disease

These should be monitored by symptoms, liver enzymes (ALT, AST, alkaline phosphatase), bilirubin, lipase, and amylase and subjects should be treated according to the Investigator's judgement.

Fluid Overload, Hypotension and Persistent Abdominal Pain

Subjects will be monitored closely for signs and symptoms related to fluid overload (e.g., edema, due to increased absorption), hypotension and persistent abdominal pain. The Investigator will document any cases and manage as per clinical practice for the subject accordingly.

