6.2.2 Prohibited Previous and Concomitant Medication

Any use of growth hormone, glutamine or growth factors such as GLP-1, GLP-2 or analogues thereof is prohibited within the last 3 months prior to Screening and throughout the trial.

Systemic corticosteroids, methotrexate, cyclosporine, tacrolimus, sirolimus, infliximab or other biologic therapy/immune modifiers are prohibited within 30 days of Screening and throughout the trial.

Use of prescription or non-prescription drugs and dietary and herbal supplements are prohibited within 28 days or five half-lives, if known, (whichever is longer) prior to the first dose of IMP unless deemed necessary by the Investigator for the treatment of concurrent disease consistent with subjects with renal impairment.

Acetaminophen may be used at doses of ≤ 3 g/day.

No new medication should be started during the trial, unless medically necessary and prescribed by the Investigator or another qualified designee involved in the subject's care and being aware of the subject's participation in the trial.

All concomitant treatments taken during the trial must be recorded with indication, daily dose, and start and stop dates of administration. Concomitant drug and non-drug treatment will be collected. All subjects will be questioned about concomitant treatment at each clinic visit.

Treatments taken within 28 days before the first dose of IMP will be documented as a prior treatment. Treatments taken after the first dose of IMP will be documented as concomitant treatments.

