- The Investigator or designee will discuss with the subject the need to use highly effective contraception consistently and correctly according to the contraception guidelines and will confirm highly effective, proper contraception is being used up to 1 month after EOT
- Review concomitant treatments
- Subjects will be instructed on all pertinent lifestyle requirements and restrictions
- Injection site assessment at approximately 168 hours post-dose
- Discharge from CRU confinement

If a subject has any clinically significant trial-related abnormalities at the conclusion of a scheduled inpatient portion of the trial, the Safety Medical Monitor (or designated representative from the Sponsor) should be notified and the subject may be asked to remain in the CRU until such abnormalities are deemed not clinically significant, or it is safe for outpatient follow-up. If the subject is unable or unwilling to remain in the CRU and/or when outpatient follow-up is deemed appropriate, the Safety Medical Monitor (or designated representative) should be notified and the Investigator should make every effort to arrange follow-up evaluations at appropriate intervals to document the course of the abnormalities.

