10.3.3 Reporting of Serious Adverse Events

All SAEs must be reported immediately and within a maximum of 24 hours to the CRO and thereafter the CRO will report to the Sponsor of the trial.

Serious adverse event primary information should be collected through the eCRF and the reporting is done via paper form, which can be submitted via email or fax to PRA Safety.

The contact information is:

- North/South America
- Fax: [REDACTED]
- Email: [REDACTED]

The Sponsor/CRO will re-evaluate the SAE and return the form to the site, requesting clarification or follow-up information if needed. After the initial SAE report, the Investigator is required, proactively, to provide further information regarding the subject's condition.

Serious AEs resulting in death will be reported to the IRB within 7 days.

The minimum data required for a report is:

- Subject identifier (ID)
- Trial ID
- Date of enrolment
- Date and time of start of SAE
- Description of SAE
- Severity of SAE
- Assessment of causality relationship to IMP
- Name and contact details of person reporting the event

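### Protocol Section 10.2 gives opposite SAE classifications to an unplanned admission treated with a non-permitted drug, so such an event can lose SAE status and expedited reporting

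*Protocol*

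**What the plan says.** Protocol Section 10.2 defines an SAE by six criteria, one of which is that the event requires in-patient hospitalization or prolongs an existing one. A list of six kinds of admission that fall outside the definition follows.

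- The first bullet exempts elective admissions for trial treatment or procedures, then sets a limit: "all events leading to unplanned hospitalizations or unplanned prolongation of an elective hospitalization", with undesirable effects of treatment as the example given, "must be documented and reported as SAEs".
- The fifth bullet exempts admissions for pre-existing conditions, but only if they are elective and the condition has not worsened.
- The sixth and last bullet exempts "Hospitalization to facilitate treatment of disease/illness with other treatment options, although these treatments are not permitted as per the protocol". Such a case goes into the deviation log instead.

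The line directly below the list asks that doubtful events be reported on time.

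Section 6.2.2 identifies treatments that are not permitted: "Systemic corticosteroids, methotrexate, cyclosporine, tacrolimus, sirolimus, infliximab or other biologic therapy/immune modifiers are prohibited within 30 days of Screening and throughout the trial". Section 10.3.3 sets the SAE timeline: "All SAEs must be reported immediately and within a maximum of 24 hours to the CRO".

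**The concern.** Two bullets of one list apply to the same event and disagree. The last bullet does not say that it covers only planned admissions, and nothing in Section 10.2 says which bullet prevails. An investigator who goes straight to the last bullet finds an explicit exemption and an alternative place to record the case, the deviation log.

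SAE status drives the expedited safety route. Without it, an event does not enter the 24-hour report, is not considered for SUSAR reporting under Section 10.3.4, and does not appear in the SAE outputs of the SAP (Table 14.3.1.5 and the listing in Table 14.3.2). Safety is the trial's secondary objective, and with about eight subjects per cohort the few serious events that occur need to be classified by one rule.

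**Working it through.** No alpha, power or sample-size figure is involved, so the check is textual. Take a test event: after dosing, a subject is admitted to hospital unexpectedly and stays overnight. The subject is treated with a systemic corticosteroid and recovers. The event is not life-threatening and not disabling, and the investigator does not class it as medically significant on other grounds.

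1. **SAE criterion (10.2).** The event requires in-patient hospitalization. Result: SAE.
2. **First bullet of the exemption list (10.2).** The admission is unplanned, so the mandatory rule applies. Result: SAE.
3. **Last bullet of the list (10.2).** The admission is for treatment of an illness with a drug that Section 6.2.2 prohibits. Result: not an SAE; recorded as a deviation.
4. **Is the last bullet limited?** The bullet directly above it is limited to elective admissions and unworsened pre-existing conditions. The last bullet has neither limit, and no order of precedence is stated. Steps 2 and 3 therefore conflict on the wording.
5. **Is the treatment really not permitted?** The corticosteroid and immune-modifier sentence in 6.2.2 has no exception of its own. A later sentence in 6.2.2 allows new medication when medically necessary, but does not say that it overrides the named prohibition. The exception for treating AEs in 6.2.2.1 is written for Cohort 2 only. Section 6.2.2.2, for the impaired cohorts, deals with stable background medication. The class of events is therefore narrow but not empty.
6. **What is lost if step 3 is followed?**
   - The 24-hour report (10.3.3). The event instead follows the AE data-entry timeline in the clinical trial agreement (10.3.1), or two weeks if it is an AESI (10.3.2).
   - SUSAR assessment (10.3.4). Fatal and life-threatening events are SAEs whether or not there is an admission, so the 7-day clock is not exposed. The 15-day clock for other SUSARs is.
   - Entry in SAP Tables 14.3.1.5 and 14.3.2.
7. **What is kept?** The event is collected as an AE (10.1) and entered in the eCRF (10.3.1). If treatment-emergent, it is counted in the TEAE tables by relationship and severity (SAP 17.1.1). It is listed with all AEs (Listing 16.2.7.1) and counted as an AESI where it is one. The enrolment and dosing interruption rule in Section 5.3 works on AESI type and CTCAE grade, so it does not depend on SAE status.

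**The case against.** The strongest reply is that the protocol already covers the case. The first bullet is mandatory and names undesirable effects of treatment; the last bullet can be read as covering admissions arranged to give another therapy; and the line below the list favours reporting when in doubt. An event needing medical intervention to prevent a serious outcome may also qualify as medically significant without any reference to admission. All of this stands as mitigation and explains why few events are exposed. It does not remove the conflict: the planned-admission reading is not stated, and the doubt line helps only an investigator who notices that two bullets apply.

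Several stronger readings are tempting, and the documents do not support them.

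- **A reader might infer that a serious reaction could go unreported and uncounted altogether.** It would not. It stays in the AE reporting, tables and listings described above; what is at risk is SAE status and expedited reporting.
- **A reader might infer a 14-day delay in place of 1 day.** The two-week limit applies only to AESIs. The timeline for other AEs is in an agreement outside these documents.
- **A reader might cite 1/8 = 12.5 percentage points as the distortion in a cohort's SAE incidence.** That is the weight of any single affected subject in a cohort of eight. It does not measure this defect, and the SAE table is descriptive, with no formal testing (SAP 9.4.3).
- **A reader might infer that the exempted cases are the gravest ones, or fall mainly in the renally impaired cohorts, or will be classified differently at the two sites.** No text or figure in the documents shows any of these.
- **A reader might see a second contradiction over prolonged stays.** Section 7.3.9 says that "the subject may be asked to remain in the CRU until such abnormalities are deemed not clinically significant", and Section 10.2 treats routine and unplanned prolongation differently. Those two terms describe different situations, and the Safety Medical Monitor (or a sponsor representative) should be notified of the abnormality. Whether such an extension counts as prolongation is left open, which is a minor gap in clarity.

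**Conclusion.** The contradiction is real on the wording and confined to a narrow class: unplanned in-patient admissions treated with something the protocol does not permit. For these, Section 10.2 gives two opposite classifications. If the exemption is followed, the event remains an AE but can miss the 24-hour report, SUSAR assessment and the SAE outputs, unless another seriousness criterion or the doubt line catches it.

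The documents give no admission rate and no rate of prohibited-drug use, so the expected number of affected events cannot be calculated; it is probably small. The conclusion assumes that the last bullet is read as written, without an implied limit to planned admissions, and that the corticosteroid and immune-modifier prohibition is read without an implied exception for treating AEs. It should be corrected because a stated exemption can switch off expedited reporting and the correction is almost free. It does not threaten the primary PK analysis.

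**What to change.** In Section 10.2, make the last exemption bullet expressly subject to the unplanned-hospitalization rule in the first bullet, or delete it. State that a non-permitted treatment given during such an admission is recorded as a protocol deviation in addition to SAE reporting, not instead of it. Leave the other exemptions as they are, including social reasons and stays without an overnight component, so that the clarified rule does not collide with them. This applies the protocol's own existing rule and takes no position on which treatments should be permitted.

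As a separate minor clarification, add one sentence saying whether an extension of CRU confinement under Section 7.3.9 counts, by itself, as prolongation of hospitalization.

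The cost is two or three sentences in a protocol amendment and in site instructions. No new data are collected and no SAP output changes. The downside is possibly an occasional extra SAE form.
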